9.1 TREATMENT/INTERVENTION PLAN

9.2 Aromatase Inhibitor Administration

This clinical trial was initially comprised of two arms, one for BYL719 in combination with letrozole (Arm A), and another for BYL719 in combination with exemestane (Arm B). As of January 2014, the study is being amended to include two additional arms, and patients will no longer be enrolled onto Arms A or B. On Arm C, patients will receive intermittent BYL719 (7 days on, 7 days off) in combination with daily letrozole, and on Arm D, patients will receive intermittent BYL719 (5 days on, 2 days off) in combination with daily exemestane. Patients will be eligible for only one of the two arms, Arm C or Arm D, depending on which AI

(letrozole or exemestane) they were taking before study enrollment (i.e., a patient who was taking letrozole will continue to take letrozole, and a patient who was taking exemestane will continue to take exemestane). Patients will not be randomized to one of the two arms.

Letrozole or exemestane will be self-administered by the study patients orally once daily. . On days that patients are taking BYL719, aromatase inhibitor should be swallowed concomitantly with BYL719, or less than 5 minutes apart, at approximately the same time every day. The recommended time of administration is approximately 9 am (+/- 2 hrs). On a day of PK bloodwork, patients will take the scheduled dose in clinic. Treatment doses for each AI will be fixed at the established dose (see Table 9-1 below). There will be no dose escalation or dose reduction for letrozole or exemestane.

Table 9-1

Arm	AI dose	BYL719 schedule (dose per cohort)
A	Letrozole 2.5mg orally once daily	Days 1-28 of 28 day cycle
B	Exemestane 25mg orally once daily	Days 1-28 of 28 day cycle
C	Letrozole 2.5mg orally once daily	Days 1-7, 15-21 of 28 day cycle
D	Exemestane 25mg orally once daily	Days 1-5, 8-12, 15-19, 22-26 of 28 day cycle

9.3 BYL719 Administration

BYL719 will be taken orally (see Table 9-1, Table 9-2, and Section 9.4 for dose-finding schema). A new bottle of medication at the appropriate dose level will be dispensed on Day 1 of each 28-day cycle, regardless of the number of tablets remaining in the bottle from the previous cycle. For patients receiving treatment under Amendment 13; medication bottles will be dispensed on Day 1 of every other 28 day cycle such that each dispensation will provide enough tablets for two cycles. Patients will be provided with an adequate supply of BYL719 for self-administration at home until at least their next scheduled study visit. All dosages prescribed and dispensed to the patient and any dose change or interruption must be recorded appropriately.

Arms C and D

COHORT	BYL719 dose
+2	350mg
+1	300mg
0 (starting dose)	250mg
-1	200mg

Patients may be seen up to 7 days prior to or following the planned cycle start for the purpose of scheduling/conflicts. This window is also applicable to patients who are being seen in clinic every two cycles under Amendment 13. In the case of such changes for

scheduling/conflicts, BYL719 should continue to be self-administered. Day 1 of each cycle will remain as every 28 days.

Patients will be instructed to take BYL719 as per protocol.

The following general guidelines should be followed for BYL administration:

- Patients should be instructed to take one or more tablets of BYL719 together with a glass of water (~250 ml or ~8 fluid ounces) daily in the morning approximately 1 hour after start of a light breakfast (e.g., consisting of non-grapefruit based juice, toast and jam) at approximately the same time each day (recommended 8AM +/- 1 hour), except on the days blood collection is scheduled at the clinic, at which time the patients should take their doses at the clinic. A light breakfast is defined as approximately 500 calories, with approximately 75% from carbohydrates and approximately 25% from protein and/or fat.
- Patients should not eat for 1 hour after the administration of BYL719.
- If by noon the patient forgets to take the study drug (BYL719), then the dose should be withheld that day. Missed doses should not be made up. If, for any reason, a breakfast was not consumed, then the patient should still take the scheduled morning dose of study drug with a glass of water.
- Patients should be instructed to swallow the tablets and not to chew or crush them.
- Patients should be dosed in a staggered manner at least 1 hour before or 10 hours after dosing with medicinal products that may alter the pH of the upper GI tract.
- Patients should record if the dose was taken or not in the patient diary.
- If vomiting occurs during the course of treatment, no re-dosing of the patient is allowed before the next scheduled dose. The occurrence and frequency of any vomiting and/or diarrhea (or increase stool frequency) during the treatment must be noted in the adverse events section of the eCRF.
- Patients must avoid consumption of Seville orange (and juice), grapefruit or grapefruit juice, grapefruit hybrids, pummelos, starfruits and cranberry juice from 7 days prior to the first dose of study drug and during the entire study treatment period due to potential CYP3A interaction. Regular orange (*Citrus X sinensis*) juice is allowed.

On a day of scheduled fasting glucose testing, patients must be fasting overnight for at least 8 hours prior to the blood collection. A light breakfast should be consumed after fasting glucose blood draw. BYL719 will be taken in clinic approximately 1 hour after the start of breakfast. Patients should then fast for 1 hour after the administration of BYL719.

Fasting glucose testing and PK sampling may be performed on the same day: fasting overnight for at least 8 hours → fasting blood collection and pre-dose PK sample → light breakfast → 1 hour wait → BYL719 oral administration → post-dose PK sample at the appropriate time intervals (see Section 10.11).

Patients will be given a medication diary to record the date and time of their BYL719 dose each day (Appendix H and Appendix I).

9.4 Dose-Limiting Toxicity (DLT) Definition

Toxicity will be tabulated using the NCI Common Toxicity Criteria (CTCAE), version 4.0. A dose-limiting toxicity (DLT) is defined as an adverse event or abnormal laboratory value assessed as at least possibly related to the study medication, meeting any of the criteria listed in the table below, and occurring during Cycle 1 (≤ 28 days following the first dose of BYL719, including those in which the event started in Cycle 1 and the confirmation of the DLT occurs in a subsequent cycle). Whenever a patient experiences toxicity that fulfills the criteria for a DLT, treatment with the study drug will be interrupted and the toxicity will be followed up (see toxicity management guidelines in Section 10).

As an additional safety measure to assess for late-appearing toxicity, a confirmatory safety assessment will be performed at the end of Cycle 2. If dose-limiting toxicity is observed between 28 days and 56 days, then safety data will be reviewed by the Principle Investigator and Novartis, and this information will inform the dose-finding cohorts.

Table 9-2 Dose-Limiting Toxicity Criteria

Toxicity	DLT criteria
Blood and lymphatic system disorders	Anemia CTCAE Grade 3 for > 14 consecutive days
	Anemia CTCAE Grade 4
	Febrile neutropenia CTCAE Grade ≥ 3
	Neutropenia CTCAE Grade 3 for > 7 consecutive days
	Neutropenia CTCAE Grade 4
	Thrombocytopenia CTCAE Grade 3 for > 7 consecutive days and/or with signs of clinically significant bleeding
	Thrombocytopenia CTCAE Grade 4
Cardiac disorders	Cardiac toxicity CTCAE Grade ≥ 3 or cardiac event that is symptomatic or requires medical intervention
	Clinical signs of cardiac disease, such as unstable angina or myocardial infarction, or Troponin CTCAE Grade 3 (confirmed with a repeat Troponin within 24 hrs)
	ECG QTc interval prolonged CTCAE Grade ≥ 3
Vascular disorders/ Hypertension	Persistent hypertension CTCAE Grade ≥ 3 requiring more than one drug or more intensive therapy than previously
General disorders and administration site conditions	Fatigue CTCAE Grade 3 for > 7 consecutive days
Skin and subcutaneous tissue disorders ^a : Rash and/or photosensitivity	Rash or photosensitivity CTCAE Grade 3 for >7 consecutive days despite skin toxicity treatment, or any second or third occurrence of CTCAE Grade 3 rash regardless of duration
	Rash or photosensitivity CTCAE Grade 4
Metabolism and nutrition disorders: Hyperglycemia ^b	Hyperglycemia Grade 3(fasting plasma glucose 250 – 500mg/dL) (confirmed with a repeat fasting plasma glucose test within 48 hours) that does not resolve to grade 0 within 14 consecutive days (after initiation of oral anti-diabetic treatment)
	Hyperglycemia Grade 4
	Hyperglycemia leading to diabetic keto-acidosis, hospitalization for IV insulin infusion, or non-ketotic coma
GI disorders ^a	Diarrhea CTCAE Grade ≥ 3 for ≥ 48 hrs, despite the use of anti-diarrhea therapy
	Nausea/vomiting CTCAE Grade ≥ 3 for ≥ 48 hrs, despite the use of anti-emetic therapy
	Pancreatitis CTCAE Grade ≥ 3
Eye disorder	CTCAE Grade ≥ 3

Toxicity	DLT criteria
Blood chemistries ^c	Blood bilirubin ^d CTCAE Grade 2 for > 7 consecutive days
	Blood bilirubin ^d CTCAE Grade ≥ 3
	AST or ALT CTCAE Grade ≥ 3 in conjunction with blood bilirubin ^d CTCAE Grade ≥ 2 of any duration
	AST or ALT CTCAE Grade 3 for > 7 consecutive days
	AST or ALT CTCAE Grade 4
	Serum alkaline phosphatase CTCAE Grade 4
	Serum lipase and/or serum amylase (asymptomatic) CTCAE Grade 3 for > 7 consecutive days
	Serum lipase and/or serum amylase (asymptomatic) CTCAE Grade 4
	Serum creatinine CTCAE Grade 2 for > 7 consecutive days
	Serum creatinine CTCAE Grade ≥ 3
Other hematologic and non-hematologic toxicities	Any other clinically significant CTCAE ≥ Grade 3 toxicity
	Any intolerable CTCAE Grade 2 toxicity
	Apart from the criteria listed above, if a lower grade AE leads to a dose interruption of more than 7 consecutive days of BYL719, this AE will be considered as DLT

^a Patients will receive prophylactic treatment for rash with an antihistamine beginning on cycle 1 day 1. Patients will not initially receive prophylactic treatment for nausea/vomiting during Cycle 1. However, prophylactic treatment may be initiated in all patients at the dose level where these toxicities have been observed and in all further patients if at least 1 patient has experienced nausea/vomiting CTCAE Grade ≥ 3 or if at least 2 patients experienced skin toxicity or nausea/vomiting CTCAE Grade ≥ 2 (see Section 11.2 and Table 10-2 for further details). Anti-emetics may be applied for treatment if the patient has experienced nausea/vomiting CTCAE Grade ≥ 1, at the discretion of the physician.
 
^bHyperglycemia occurring during corticosteroids administration will be only be considered DLT if not resolved within 5 days after the end of corticosteroid treatment.
 
^c For any hepatic toxicity CTCAE Grade 4, or CTCAE Grade 3 that does not resolve within 7 days to CTCAE Grade ≤ 1 (or CTCAE Grade ≤ 2 if liver infiltration with tumor present), an abdominal CT scan should be performed to assess if it is related to disease progression.
 
^d Refers to total bilirubin.
	

9.5 Dose-Finding Phase

The dose-finding phase will follow a standard 3 + 3 design. A treatment cycle will consist of 28 days. Patients will continue on treatment until progression of disease or unacceptable toxicity.

For Arms A and B, the starting dose of BYL719 for the first cohort (Cohort 0) will be 300mg daily, which is 75% of the MTD from the phase I study. Treatment doses for BYL719 for each cohort are presented below:

Table 9-3 Dose-Finding Cohorts for Arms A and B

COHORT	BYL719 dose
+2	400mg orally once daily (100% of MTD for single agent BYL719)
+1	350mg orally once daily (87.5% of MTD for single agent BYL719)
0 (starting dose)	300mg orally once daily (75% of MTD for single agent BYL719)
-1	250mg orally once daily (62.5% of MTD for single agent BYL719)
-2	200mg orally once daily (50% of MTD for single agent BYL719)

For Arms C and D, the starting dose of BYL719 for the first cohort (Cohort 0) will be 250mg daily. Treatment doses for BYL719 for each cohort on Arms C and D are shown below:

Table 9-4 Dose-Finding Cohorts for Arms C and D

COHORT	BYL719 dose
+2	350mg
+1	300mg
0 (starting dose)	250mg
-1	200mg

During the dose-finding phase, a periodic teleconference will be held at least monthly with the primary investigator and Novartis to review toxicity data and ensure patient safety moving forward.

Dose escalation or de-escalation schema:

On each arm, three patients will be enrolled onto Cohort 0 at the starting BYL719 dose. All patients within a cohort will be observed for toxicity for one cycle (28 days) prior to entering additional patients. If a patient discontinues study participation during the first cycle (within 28 days of starting study treatment) for reasons unrelated to an adverse event, an additional patient may be enrolled to replace that subject. Between 6 and 15 patients in each arm will be necessary to determine the recommended phase II dose of BYL719 in combination with letrozole or exemestane.

There will be no inpatient dose escalation. Inpatient dose reductions of BYL719 will not be allowed during Cycle 1 (within 28 days of starting study treatment), unless a DLT has occurred and been counted towards informing enrollment of future cohorts of patients. This is in order to accurately determine the safe and tolerable dose of BYL719 when used in combination with letrozole or exemestane.

Schema for Cohort 0:

If none of the initial three patients in Cohort 0 experience dose-limited toxicity (DLT), as defined above, then three new patients will be enrolled in Cohort +1 (dose escalation).

If one of the initial three patients in Cohort 0 experiences DLT, then up to three additional patients will be treated at the same dose level. If no more than one of six patients in Cohort 0 experiences DLT, then three new patients will be enrolled in Cohort +1 (dose escalation).

If two or more patients in Cohort 0 experience DLT, then three new patients will be enrolled in Cohort -1 (dose de-escalation).

Schema for Cohort +1:

If none of the initial three patients in Cohort +1 experience dose-limited toxicity (DLT), as defined above, then three new patients will be enrolled in Cohort +2 (dose escalation).

If one of the initial three patients in Cohort +1 experiences DLT, then up to three additional patients will be treated at the same dose level. If no more than one of six patients in Cohort +1 experiences DLT, then three new patients will be enrolled in Cohort +2 (dose escalation).

If two or more patients in Cohort +1 experience DLT, then the dose level in Cohort 0 will be re-considered as the recommended phase II dose. If only three patients were treated in Cohort 0, then up to three additional patients will be accrued to that dose level. If no more than one of six patients in Cohort 0 experiences DLT, then that dose level will be confirmed as the recommended phase II dose of BYL719 in this combination.

Schema for Cohort +2:

If none or one of the initial three patients in Cohort +2 experience DLT, then up to three additional patients will be treated at the same dose level. If no more than one of six patients in Cohort +2 experiences DLT, then that dose level will be the recommended phase II dose of BYL719 in this combination.

If two or more patients in Cohort +2 experience DLT, then the dose studied in Cohort +1 will be re-considered. If only three patients were treated in Cohort +1, then up to three additional patients will be accrued to that dose level. If no more than one of six patients in Cohort +1 experiences DLT, then that dose level will be confirmed as the recommended phase II dose of BYL719 in this combination.

Schema for Cohort -1:

If none or one of the initial three patients in Cohort -1 experience DLT, then up to three additional patients will be treated at the same dose level. If no more than one of six patients in Cohort -1 experiences DLT, then that dose level will be confirmed as the recommended phase II dose of BYL719 in this combination. If two or more patients in Cohort -1 experience DLT, then three new patients will be enrolled in Cohort -2.

Schema for Cohort -2:

If none or one of the initial three patients in Cohort -2 experience DLT, then up to three additional patients will be treated at the same dose level. If no more than one of six patients in Cohort -2 experiences DLT, then that dose level will be confirmed as the recommended phase II dose of BYL719 in this combination. If two or more patients in Cohort -2 experience DLT, then we will conclude that the combination is not feasible and will discontinue the affected arm of the trial. If this occurs, accrual onto the unaffected arm will be halted until safety data is reviewed by the primary investigator and Novartis to determine whether to continue or close the unaffected arm of the trial.

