B	Exemestane 25mg orally once daily	Days 1-28 of 28 day cycle
C	Letrozole 2.5mg orally once daily	Days 1-7, 15-21 of 28 day cycle
D	Exemestane 25mg orally once daily	Days 1-5, 8-12, 15-19, 22-26 of 28 day cycle

The dose-finding phase will follow a standard 3 + 3 design, according to the cohorts in the tables below. The starting dose of BYL719 in Arms A and B will be 300mg daily, which is 75% of the MTD from the single agent phase I study. The starting dose of BYL719 in Arms C and D will be 250mg daily.

Arms A and B

[figure not shown]
COHORT	BYL719 dose
+2	400mg orally once daily (100% of MTD for single agent BYL719)
+1	350mg orally once daily (87.5% of MTD for single agent BYL719)
0 (starting dose)	300mg orally once daily (75% of MTD for single agent BYL719)
-1	250mg orally once daily (62.5% of MTD for single agent BYL719)
-2	200mg orally once daily (50% of MTD for single agent BYL719)

Arms C and D

COHORT	BYL719 dose
+2	350mg
+1	300mg
0 (starting dose)	250mg
-1	200mg

Tumor tissue biopsies will be obtained to further define the biology of AI-resistance in metastatic ER+ breast cancer, and to evaluate predictive and pharmacodynamic biomarkers of treatment with BYL719 (see schema on following page).

We will no longer accrue to Arm A or Arm B. For Arm C and Arm D, we anticipate 4-18 patients per arm for the dose-finding phase of the trial, and we estimate an accrual rate of 2 patients per month, with a total time of 1 year to complete. We anticipate 20 patients for the expansion phase of the trial (10 patients in each arm), which will require an additional 1 year to complete.

^aNumbers represent priority order if insufficient tumor tissue is present in the biopsy for all correlatives

^bPre-treatment biopsy is preferred for the exploratory objectives being studied. We anticipate that tumor tissue may be insufficient in up to 3 biopsies, in which case these analyses may be performed on an archival primary or metastatic tumor specimen.

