4.0 OVERVIEW OF STUDY DESIGN/INTERVENTION

[figure not shown]
This is a single institution phase I dose-finding study with an expansion cohort. The primary objective is to determine the recommended phase II dose of BYL719 when administered in combination with either letrozole or exemestane to patients with HR+ locally-advanced or metastatic breast cancer. As of January 2014, this trial is being amended such that an additional primary objective is to determine the recommended phase II dose of BYL719 administered in a 7 day on, 7 day off schedule, in combination with daily letrozole, and the recommended phase II dose of BYL719 administered on a 5 day on, 2 day off schedule, in combination with daily exemestane. An expansion cohort for Arms C and D will be treated at the final dose level to further define the safety and feasibility of each combination, and to estimate efficacy.

This clinical trial was initially comprised of two arms, one for daily BYL719 in combination with letrozole (Arm A) and another for BYL719 in combination with exemestane (Arm B). As of January 2014, Arms A and B will no longer accrue patients and the study will be amended to include Arms C and D. Arm C will involve letrozole with BYL719 given on days 1-7 and 15-21 of a 28 day cycle. Arm D will involve exemestane with BYL719 given on days 1-5, 8-12, 15-19, 22-26 of a 28 day cycle. The figure below shows the overall study scheme for Arms C and D. Patients will be eligible for only one of the two arms depending on which AI (letrozole or exemestane) they were taking before study enrollment. Patients will not be randomized to one of the two arms.

Dose-escalation phase

Dose-expansion phase

For both the dose-finding and expansion phases of Arms C and D, patients may have stable or progressive disease on letrozole or exemestane, and BYL719 will be added. We anticipate 12-30 patients for the dose-finding phase of the trial (6-15 patients in Arm C, and 6-15 patients in Arm D), and 20 patients for the expansion phase of the trial (10 patients in Arm C, and 10 patients in Arm D).

As of June 2015, the recommended phase II dose of BYL719 has been determined to be 350mg for Arm D and we are currently enrolling 10 patients to the corresponding arm in the expansion phase of the study. Dose Expansion to Arm C is currently on hold.

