For each patient, a maximum of two dose reductions (minimum dose of BYL719 for this study is 200mg daily on Arm A and Arm B, and 150mg intermittently on Arm C and Arm D) will be allowed after which the patient will be discontinued from the study treatment. Dose reduction for BYL719 means treatment at the next lower dose level of BYL719 (e.g., 300mg daily if the prior dose was 350mg daily, and 250mg daily if the prior dose was 300mg daily). In addition, a patient must discontinue treatment if, after treatment is resumed at a lower dose, the same toxicity reoccurs with the same or worse severity. If, after interruption of treatment and resolution, treatment is resumed at the same dose following the criteria in Table 10-2, and the same toxicity reoccurs with the same severity, next treatment re-initiation must resume at the next lower dose level irrespective of duration.

There will be no inpatient dose escalation for BYL719. For each patient, once a dose level reduction of BYL719 has occurred, the dose level may not be re-escalated during subsequent treatment cycles with the study drug.

There will be no dose escalation or dose reduction for letrozole or exemestane.

For specific guidelines related to hyperglycemia, see Section 10.10.3.

Table 10-2 Criteria for interruption and re-initiation BYL719 treatment

Recommended Dose Modifications for BYL719	
Worst Toxicity CTCAE v4.03 Grade (unless otherwise specified)	Recommended Dose Modifications any time during a cycle of therapy
BLOOD AND LYMPHATIC SYSTEM DISORDER	
Anemia	
Grade 1 (Hgb < LLN-10.0 g/dL)	Maintain dose level of BYL719.
Grade 2 (Hgb < 10.0 g/dL - 8.0 g/dL)	Maintain dose level of BYL719.

Recommended Dose Modifications for BYL719	
Worst Toxicity CTCAE v4.03 Grade (unless otherwise specified)	Recommended Dose Modifications any time during a cycle of therapy
Grade 3 (Hgb < 8.0 g/dL); transfusion indicated	Omit dose of BYL719 until resolved to CTCAE Grade ≤ 1 or baseline - If resolved in ≤ 14 days, then maintain dose level of BYL719. - If resolved in > 14 days, then ↓ 1 dose level ^a of BYL719.
Grade 4 (Life threatening consequences; urgent intervention indicated)	Discontinue study treatment.

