14.2 Dose-Finding Phase

The purpose of the dose-finding portion of the study is to determine the recommended phase II dose of BYL719 in combination with a fixed dose of either letrozole or exemestane. For Arm A and Arm B, the five proposed doses of BYL719 are 200mg, 250mg, 300mg, 350mg or 400mg. For Arms C and D, the five proposed doses of BYL719 are 150mg, 200mg, 250mg, 300mg, and 350mg.

The plans for dose escalation or de-escalation consist of entering patients in cohorts of three. The specific details are given in Section 9.4. Dose-limiting toxicities are defined in Section 9.3. All patients within a cohort will be observed for toxicity for one cycle (28 days) prior to entering patients at the next dose level. If a patient discontinues study participation during the first cycle (within 28 days of starting study treatment) for reasons unrelated to an adverse event or disease progression, an additional patient may be enrolled to replace that subject. We expect this early dropout to be a rare event, occurring 5% of the time, and will be examined closely as a source for potential bias. Otherwise, all patients who receive at least one dose of BYL719 in combination with letrozole or exemestane will be evaluable for toxicity. All patients who receive at least one week of BYL719 in combination with letrozole or exemestane will be evaluable for response.

The probability that dose escalation or de-escalation will occur at any stage during this portion of the study is a function of the underlying DLT rate at the current dose level. This probability can be calculated as the sum of the binomial probabilities of the following two outcomes that would permit escalation to occur:

1. No DLT observed in the first three patients.
2. One DLT is observed in the first three patients followed by no DLT observed in three additional patients at the same dose level.

The true risk of toxicity is expected to be in the range of 10%-40%. The following table shows the corresponding probabilities of dose escalation:

True Risk of Toxicity	.10	.20	.30	.40
Probability of Escalation	.91	.71	.49	.31

These numbers show that the probability of escalating to the next dose level is large when the underlying true toxicity rate is small and the probability of escalating decreases appropriately as the true toxicity rate increases.

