Between 2-6 patients will be treated at each dose level. Assuming 4 dose levels, this portion of the trial will require a minimum of 4 and a maximum of 24 patients for each arm. If 2 or more patients in the lowest dose cohort (Cohort -2 for Arms A and B, and Cohort -1 for Arms C and D) for either arm experience DLT, then we will conclude that the combination is not

feasible and will discontinue the affected arm of the trial. If this occurs, accrual onto the unaffected arm will be halted until safety data is reviewed by the primary investigator and Novartis to determine whether to continue or close the unaffected arm of the trial.

We expect both arms (Arm C and Arm D) to accrue simultaneously, as letrozole is typically given first-line for HR+ metastatic breast cancer, while exemestane is more often used in the second-line setting. With an expected accrual rate of at least 2 patients per month, it is expected that the dose-finding portion of the trial will take less than 1 year. This allows each 3-patient cohort to be observed for 28 days, the length of time for treatment with one cycle of therapy, prior to additional patients being accrued.

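### For Arms C and D, two or more DLTs at Cohort -1 open an undefined Cohort -2 in Section 9.5 but close the arm in Section 14.2, and the stated dose lists and patient ranges do not agree

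*Combined protocol and SAP*

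**What the plan says.** Section 9.5 sets out the escalation schema once, for each arm, directly after Table 9-4. Table 9-4 gives Arms C and D four cohorts: +2 (350 mg), +1 (300 mg), 0 (250 mg) and -1 (200 mg). The tables in Sections 1.0 and 9.3 show the same four. The schema nevertheless states "If two or more patients in Cohort -1 experience DLT, then three new patients will be enrolled in Cohort -2", and it closes an arm only after two or more DLTs at Cohort -2.

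Section 14.2 names the lowest cohort as -2 for Arms A and B and -1 for Arms C and D. Its rule for two or more DLTs there reads "Cohort -1 for Arms C and D) for either arm experience DLT, then we will conclude that the combination is not" feasible; the arm is then discontinued and the other arm is halted for safety review.

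On doses, Section 14.2 says "For Arms C and D, the five proposed doses of BYL719 are 150mg, 200mg, 250mg, 300mg, and 350mg", and then "Assuming 4 dose levels, this portion of the trial will require a minimum of 4 and a maximum of 24 patients for each arm". Section 10.10.2 gives the minimum dose for individual reductions as "200mg daily on Arm A and Arm B, and 150mg intermittently on Arm C and Arm D".

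On patient numbers per arm:
- Section 1.0: "we anticipate 4-18 patients per arm for the dose-finding phase of the trial".
- Section 4.0: "We anticipate 12-30 patients for the dose-finding phase of the trial (6-15 patients in Arm C, and 6-15 patients in Arm D".
- Section 9.5: "Between 6 and 15 patients in each arm will be necessary to determine the recommended phase II dose of BYL719".
- Sections 14.1 and 14.2: 4 to 24.

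**The concern.** For Arms C and D the same observation leads to opposite actions. Under Section 9.5 the arm continues at a lower dose that no table defines. Under Section 14.2 the arm ends and its partner pauses. This is the decision rule for the primary objective, so a reader should be able to reconstruct it without guessing.

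The 150 mg dose is the natural candidate for Cohort -2, but nothing labels it so. It appears in the Section 14.2 dose list, yet the sizing in that section leaves it out, and its only other role is as a floor for individual dose reductions. The three patient ranges cannot all describe one schema, and the Section 9.5 figure is worded as a requirement rather than a forecast.

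**Working it through.** **Reproducing the plan's own figures.** The chance of escalating at DLT rate p is E(p) = (1-p)³ + 3p(1-p)²(1-p)³. At p = .10, .20, .30 and .40 this gives .906, .709, .494 and .309, matching the Section 14.2 table (.91, .71, .49, .31). The 4-24 range also reproduces for four levels: the maximum is 4 × 6 = 24. The minimum is two patients at Cohort 0 plus two at Cohort -1 = 4, if a cohort closes at its second DLT. That convention fits the 2 to 6 patients per level stated in Section 14.2. With full cohorts of three the minimum is 6.

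**Patients needed to declare a recommended dose (four levels).**
- Fewest, full cohorts: 3 at Cohort 0 with two or more DLTs, then 6 at Cohort -1 = 9. Equally, 3 at Cohort 0, 3 at +1, then 3 more at 0 = 9.
- Fewest, closing at the second DLT: 2 + 6 = 8, or 3 + 2 + 3 = 8.
- Six patients can only close an arm.
- Most, for a dose at Cohort +2: 6 + 6 + 6 = 18. This is also the overall maximum if a reconsidered dose that fails is not stepped down further, and it is the only reading that gives 4-18.
- Most, with step-down: 3 at Cohort 0, 3 at +1, 6 at +2 (fails), 3 more at +1 (fails), 3 more at 0 (fails), 6 at -1 = 24.
- With a fifth level at 150 mg: 5 × 6 = 30 at most. An arm then takes 6-30 patients (9-30 with full cohorts), and declaring a dose takes 8-30 (9-30).

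No reading gives 6-15.

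**Chance of reaching the conflict.** The documents give only a 10%-40% range for the DLT risk, so the curves are assumptions. Let G(p) = 3p²(1-p) + p³ be the chance of two or more DLTs in three patients, and F(p) = 1 - (1-p)⁶ - 6p(1-p)⁵ the chance of two or more in six. With step-down:
- Cohort +2 fails: R₂ = F(p₂).
- Cohort +1 fails: R₁ = 1 - E(p₁) + (1-p₁)³ · R₂ · G(p₁).
- Cohort 0 fails: R₀ = 1 - E(p₀) + (1-p₀)³ · R₁ · G(p₀).
- Conflict reached: R₀ · F(p₋₁).

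At a flat 20%: R₂ = .3446; R₁ = .2914 + .512 × .3446 × .104 = .3097; R₀ = .2914 + .512 × .3097 × .104 = .3079; conflict = .3079 × .3446 = .1061. Without step-down it is .2914 × .3446 = .1004.

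If a 150 mg Cohort -2 existed, closure without a recommended dose would need a further factor F(p₋₂).

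| DLT curve | Conflict reached = closure under Section 14.2 | Closure with a 150 mg Cohort -2 |
|---|---|---|
| Flat 10% | 1.1% | 0.1% |
| Flat 20% | 10.6% | 3.7% |
| Flat 30% | 31.7% | 18.4% |
| Flat 40% | 57.3% | 44.0% |
| Rising .10/.20/.30/.40 from Cohort -1 to +2 (5% assumed at 150 mg) | 3.7% | 0.1% |

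**Chance that an arm needs more than 15 patients (four levels).** Exact enumeration of every path, in the order flat 10%, 20%, 30%, 40%, then rising:
- Step-down, full cohorts: .044, .075, .064, .040, .079.
- Step-down, closing at the second DLT: .044, .071, .056, .030, .073.
- No step-down, full cohorts: .042, .059, .037, .014, .047.
- No step-down, closing at the second DLT: .042, .059, .036, .013, .046.

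The range is about 1% to 8%.

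**The case against.** The best counter-argument is that the rule written specifically for Arms C and D is the one in Section 14.2, and that all three Arm C/D dose tables agree with it. The Cohort -2 sentence then reads as Arm A/B text that was not re-scoped when the new arms were added. Neither reading is unsafe in the sense of over-dosing: both stop treating new patients at 200 mg, and Section 9.5 requires at least monthly toxicity calls during dose finding. Section 14.2 is probably what was intended. But the schema is introduced for each arm, and Section 14.2 itself lists 150 mg as a proposed dose and refers the reader back to Section 9 for the details. The specific text therefore does not settle the matter.

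A second argument is that the effect is small. Accrual is closed, and Arm D's recommended dose is 350 mg, so this branch did not set it. The larger probabilities need a 30%-40% DLT rate at 200 mg intermittent, equal to the rate at 350 mg, which is hard to believe. Both points stand. What remains open is Arm C: its expansion is reported as on hold, and the documents do not say which cohorts it reached.

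A third argument is that Sections 1.0 and 4.0 give anticipated numbers, not bounds, and the mean per arm is only about 9 to 13 patients. That is fair for those two sections. It does not rescue Section 9.5, which says 6 to 15 will be needed. The approximate total of 38 is not in dispute.

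**Conclusion.** The inconsistency is real and should be corrected. On identical safety data, one section opens a cohort with no defined dose and another closes the arm. The chance of reaching that branch is 3.7% per arm on the rising curve and 1.1% to 57.3% on flat curves; all of these rest on assumed DLT rates. The 150 mg dose is listed as a proposed dose but is not a dose-finding cohort. The 4-24 range is correct for four levels, and 4-18 holds only without further step-down. The requirement of 6 to 15 is wrong at both ends, with the upper end exceeded in about 1% to 8% of four-level runs. The consequence today is mainly for reporting and for reconstructing the rule, above all for Arm C.

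**What to change.** Limit the Cohort -2 schema in Section 9.5 to Arms A and B, and state there that two or more DLTs at Cohort -1 close the arm in Arms C and D, as Section 14.2 says. Remove 150 mg from the Section 14.2 dose list for these arms, and say in Section 10.10.2 that it is an individual reduction dose only. Replace 4-18 and 6-15 with 4-24 per arm (8-24 to declare a recommended dose, if a cohort closes at its second DLT). Note that these ranges exclude replacements for early dropouts.

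If 150 mg was meant as a dose-finding level, instead add it to Table 9-4 as Cohort -2, move the Section 14.2 stopping rule to that level, and state 6-30 per arm (8-30 to declare a recommended dose). The chance of needing more than 15 patients then rises to about 5% to 16% with step-down.

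Leave the total of about 38 as an approximate forecast. The cost is protocol wording only, with no added patients, visits or analyses.
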